Rationale: Altered glucose and fat metabolism is most apparent in the post-prandial state, in terms of insulin resistance, β-cell failure, hyperglycemia and DNL. Our preliminary data indicates that glucose and insulin concentrations are most different between 3-4 hours following a glucose load.

The optimal timing post-drink to describe metabolomics differences is not known.

Methods: Targeted metabolomics profiles will be performed at intervals during the OGTT to determine time points that provide the biggest difference in girls with HS, hyperglycemia, inadequate β-cell response and IR. Specific targets will likely be free fatty acid and DNL markers, and will be determined from on ongoing pilot study.

II. Background and Significance:

a) Overall background:

Polycystic Ovarian Syndrome (PCOS) affects 6-10% of U.S. women, with an estimated economic burden of \$4 billion, and is increasing in prevalence in parallel with the obesity epidemic^{1,2}. PCOS includes elevated androgens, and higher rates of insulin resistance (IR), type 2 diabetes (T2D), nonalcoholic fatty liver disease (NAFLD) and cardiovascular disease (CVD)³⁻⁶. The increasing rates of obesity-related PCOS are a major contributor to the earlier onset and rising incidence of T2D, NAFLD and CVD³⁻⁷. Current PCOS therapies are marginally efficacious, and one of them, oral contraceptives, may adversely affect CVD risk⁸⁻¹⁴. *Despite the high prevalence and serious morbidity associated with PCOS, a gap exists in the current therapeutic options.*

b) Mechanisms of insulin resistance in PCOS

Alterations in hepatic metabolism may be central to IR and cardiometabolic disease in PCOS.

[figure not shown]
An estimated 50-70% of obese women with PCOS have NAFLD, compared to 20-30% of obese women without PCOS ^{7,15}. Furthermore, obese women with PCOS and NAFLD are more IR than those without NAFLD, indicating a link between NAFLD and worsening IR in PCOS ⁴. Liver enzyme concentrations, as a marker of NAFLD, independently predict dysglycemia and T2D onset¹⁶, and a new NAFLD medication decreased dysglycemia¹⁷, arguing for a tight connection between glycemia and liver health. In obese non-PCOS youth, NAFLD correlates with adipose, hepatic and muscle IR, is worsened by fructose consumption, and reversed by weight loss¹⁸⁻²¹. Animal models of primary

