We had a pilot study to perform a limited number of inpatient polysomnograms in another of our current protocols, 14-0542, which has identical inclusion criteria. Just analyzed results from 14-0542 indicate the there is a strong relationship between obstructive sleep apnea (OSA) defined as an apnea hypopnea index (AHI) of 5 events per hour or greater and fatty liver disease. Girls with OSA also had higher serum triglycerides and glucoses 2 hours after the glucola drink, despite similar BMI's (Table 1).

	Mean AHI (apnea/hour)	BMI %ile	Hepatic fat fraction (>5.5% = fatty liver)	Serum TG, mg/dL (>150 abnormal)	2 hour glucose, mg/dL (>140 pre-diabetes)
AHI >5, N=13	14.6±3.5	98±1	10.5±2.6	162±19	153±6
AHI < 5, N=13	1.3±0.4	97±1	5.3±1	110±12	131±5

Further, at least 50% of the girls studied had mild to moderate obstructive sleep apnea, and a few had severe sleep apnea, although there was a bias to performing sleep studies in girls with symptoms suggestive of OSA, so this is not a true prevalence estimate from this obese female population. Clinically, from the PI's PCOS clinic, approximate 1/3 of obese girls with PCOS are requiring continuous positive airway pressure therapy for OSA. Thus, it may be that the presence and severity of sleep apnea is a confounder for our primary outcome of altered hepatic metabolism. Accordingly, we need to quantify the presence and severity of OSA in all of our subjects to be enrolled in 16-2399.

Traditionally, inpatient overnight polysomnograms are performed in youth, to determine OSA. However, through our experience in performing these with protocol 14-0542, these can only be performed at Children's Hospital Colorado on Thursday nights, which greatly limits scheduling and enrollment. Additionally, whereas the price for these was \$500 a piece, this has now been

changed, and is currently nearly \$2,000 per patient, as a research price. Due to these limitations, we have sought alternative means of quantifying the degree and severity of OSA.

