VISIT 2 (MRI/CV VISIT)

Overall Plan: UCD Research MRI (Brain Imaging Center): Subjects will be asked to fast for 4-6 hours prior to this visit. The imaging will be of the liver. Two different studies may be conducted. One will be standard MRI of the mid abdomen to assess the amount of subcutaneous fat, visceral fat and percent liver fat. The second type of scan is optional pending scheduling. It will be ^{31}P spectroscopy to measure the concentrations of phosphate molecules including PDE, PME and PCr. This will be done twice, before and 30-45 min following a standard 75 gram glucose load. The MRI time is approximately an hour in a 2 hour visit. Vascular Endothelial function and Heart Rate Variability will be assessed with Endopat and Dynapulse, which take approximately 30 minutes.

^{31}P MRS of the Liver and Abdominal Imaging (pending scheduling)

[figure not shown]
MRS Data acquisition: Imaging and MRS will be performed on a Siemens 2.9 Tesla MRI magnet. A custom $^1\text{H}/^{31}\text{P}$ abdominal coil will be used for imaging and MRS (Clinical MR Solutions, Brookfield, WI) as in our previous ^{31}P work⁴⁰. The coil will be a concentric probe with an inner coil 16 cm in diameter (for ^{31}P) and a 20 cm outer coil (for ^1H scout imaging and shimming). A 2 cm x 2 cm x 2 cm area of focus is found in the liver in homogenous tissue for MRS, similar to our previous studies³⁸. A ^{31}P MRS scan will then be performed for baseline measurements. We will continue to work with our current collaborators [name], Assistant Professor, Department of Radiology, UC Denver Anschutz and [name], Professor, Department of Radiography, University of Alabama at Birmingham to optimize the MR signal collection. Subjects will then consume 75 grams of glucose and 25 grams of fructose and the scan will be repeated every 10 min for an hour. Visceral adiposity will be measured using the gold standard of an MRI slice at L4-L5. Hepatic fat fraction will be performed using modification of the Dixon method as in our previous studies³⁴. Hepatic fibrosis will be measured with a fibroscan sequence.

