Power calculation: The primary outcome is hepatic substrate flux pathway percentages measured as PEP, TCA and TG synthesis pathways. Power analysis is based on publications utilizing similar methods, with the Primary Aim of understanding differences in hepatic metabolism in obese girls with PCOS who either have or do not have hepatic steatosis. The reference manuscript included 13 men without HS, and 6 men with HS⁵⁰. They found that during hyper-insulinemia, glycerol related gluconeogenesis was increased, as was the PEP cycle in individuals with HS compared to those without. Utilizing the PEP value, from this paper, the difference between the group means is 3 μ mol.min.kg FFM, and the standard deviation is 2 μ mol.min.kg FFM. Differences between the two primary groups (PCOS, controls) will be assessed with a t test or for non-normally distributed data a non-parametric test such as Mann-Whitney U. With 15 untreated PCOS with HS and 15 untreated PCOS without HS, we would have a power of 0.97 to detect an alpha of 0.05. Since the reference population is men who have more uniform hormone profiles, I am choosing to be overpowered should the variability in our population be greater. As the measurement is in kg of fat free mass, we will not have to do adjustments with BMI or weight. However, as African Americans are less likely to have HS, and Hispanics more likely to have HS, if ethnicity percentages are different between groups, we will need to adjust for ethnicity in our calculations.

Secondary Aims: a) For comparison of the PCOS to control groups, individuals will be matched in terms of HS status, so that the comparison is just between the hormonal state. I am assuming that there will be less of a difference between these groups, so with a difference of 2 Umol.min.kg FFM, and the standard deviation is 2, with 20 PCOS and 20 controls, we would have a power of 0.87 to detect a alpha of 0.05. b) For comparison of treatment with either metformin or OCP's, we will compare the untreated group to the treatments individually. We will not compare the two treatments to each other. I am assuming that there will be less of a difference between these groups, so with a difference of 2 Umol.min.kg FFM, and the standard deviation is 2, with 30 PCOS and 15 in a treatment group, we would have a power of 0.87 to detect a alpha of 0.05.

All measures will be adjusted for OSA status (yes/no) and/or severity of AHI.

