Secondary outcomes include a Pearson correlation test of potentially related variables followed by targeted multiple regression to assess the relationship between hepatic fat and adipose IR, PEP, TCA, TG synthesis pathways.

Non-Isotope OGTT calculations: The Matsuda model of IR will be used but adapted for the 6.5 hour OGTT, and B-cell function [insulinogenic index ($\Delta I30/\Delta G30$) and ($\Delta C30/\Delta G30$) and disposition index ($1/I_{Fasting} \times \Delta I30/\Delta G30$) and ($1/C_{Fasting} \times \Delta C30/\Delta G30$) will be calculated^{38,49,51,52}.

Differences between groups will be evaluated with and without controlling for activity and sleep status.

Fitting glucose and glycerol concentrations curves: Using computed data points, glycerol and glucose concentrations will be fitted with an appropriate model. In control subjects, concentration typically shows 3 phases in OGTT ⁵³. Cubic polynomial, piecewise-linear, spline, and dynamic models have been used for fitting Ra in previous work^{54,55}. We will assume a cubic polynomial model; we will validate estimates obtained with the cubic polynomial model by computing comparable estimates using at least one other model form. In previous work comparing different models (piecewise-linear, cubic polynomial, dynamic), results have been relatively unaffected by choice of model. If we find that this is not the case for our data, then we would certainly consider the advantages of adopting a more complex approach, such as the state-space, for describing concentration changes.

Metabolomics data: Differences in targeted metabolic concentrations will be compared between groups, after appropriate cleaning of the data, as performed by the processing site. Changes in metabolites over time will be compared between groups, to determine the times that demonstrate the largest differences. Results will also be compared to isotopomer results, to see if a metabolomics endpoint can yield similar information to the isotopomer analysis.

Gut Microbiota: The microbiota profile is entirely exploratory, and will be related to status of hepatic steatosis and 2 hour glucose status of impaired glucose tolerance or not.

VIII. Summarize Knowledge to be Gained:

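### Matching PCOS girls and controls on steatosis status alone does not isolate the hormonal state; show a second model with the continuous MRI fat fraction beside the matched comparison

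*Combined protocol and SAP*

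**What the plan says.** Section VII, Secondary Aims a), compares PCOS girls with controls after matching: "individuals will be matched in terms of HS status, so that the comparison is just between the hormonal state". The power statement there is "with a difference of 2 Umol.min.kg FFM, and the standard deviation is 2, with 20 PCOS and 20 controls", giving 0.87 at alpha 0.05. No matching rule or tolerance is given. The same section describes steatosis as a category, "obese girls with PCOS who either have or do not have hepatic steatosis". The only cut in the protocol is the column label "Hepatic fat fraction (>5.5% = fatty liver" in the polysomnogram pilot table of the preliminary studies.

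Liver fat is nevertheless measured on a continuous scale. Under Visit 2, "Hepatic fat fraction will be performed using modification of the Dixon method as in our previous studies". The enrollment table in section III.C plans MRI for all 80 completers.

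The named test for PCOS against controls is a t test or Mann-Whitney. All measures are adjusted for OSA status and/or AHI, and ethnicity is added if it is unbalanced. Section VII also mentions group differences with and without control for activity and sleep. Hepatic fat enters only a separate analysis, "targeted multiple regression to assess the relationship between hepatic fat and adipose IR, PEP, TCA, TG synthesis pathways", where PCOS is not named as a term.

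**The concern.** Equal steatosis status is not equal liver fat. Section II.b reports: "An estimated 50-70% of obese women with PCOS have NAFLD, compared to 20-30% of obese women without PCOS". Section VIII puts NAFLD above 45% in obese girls with PCOS. If these figures reflect a fat distribution that sits higher as a whole in PCOS, a PCOS girl above the cut tends to lie further above it than her matched control, and one below the cut tends to lie closer to it. The study's main hypothesis is that steatosis goes with altered flux. A leftover fat difference would then appear as a PCOS-control flux difference in the expected direction and, under the plan's wording, be credited to hormonal state. This would happen even with perfect matching on status.

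**Working it through.** **The plan's own figure.** Difference 2, SD 2, 20 v 20: d = 2/2 = 1, noncentrality = 1 × √(20×20/40) = 3.162, 38 df. A two-sided t test gives power 0.869. The stated 0.87 is right on its inputs.

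**Inputs for the bias.** From the documents: a steatosis gap of 3 and SD of 2 (section VII, primary calculation); prevalence of 50–70% v 20–30% (adults) and above 45% (girls with PCOS). No prevalence is given for control girls. Assumed: log fat fraction is normal with the same SD in both groups; the cut is common; each group has 10 girls with and 10 without steatosis; the true hormonal effect is zero; flux is linear in log fat within strata; and within-stratum flux SD is 2.

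**Leftover fat after perfect matching.** In SD units of log fat, with prevalence p and z = Φ⁻¹(1 − p):

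- mean above the cut, relative to it = φ(z)/p − z
- mean below the cut, relative to it = −φ(z)/(1 − p) − z

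*45% v 25%.* PCOS: +0.754 and −0.845. Controls: +0.597 and −1.098. Leftover gaps: 0.157 with steatosis and 0.253 without, average 0.205. If the whole 3-unit gap runs through fat amount, the slope is 3/(0.754 + 0.845) = 1.876. Bias = 0.205 × 1.876 = 0.38.

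*70% v 20%.* PCOS: +1.021 and −0.635. Controls: +0.558 and −1.192. Gaps: 0.463 and 0.557, average 0.510. Slope = 3/1.656 = 1.812. Bias = 0.510 × 1.812 = 0.92.

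If only a share of the 3-unit gap runs through fat amount and the rest is a step at the cut, the bias shrinks in proportion: 0.3 × 0.38 is about 0.12, and 0.3 × 0.92 is about 0.28.

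**Simulation of the same set-up** (8,000 data sets per row, no hormonal effect):

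| Prevalence | Share of gap through fat | Mean estimate, steatosis term only | % of 2 | False positives, steatosis term only | False positives, log fat added |
|---|---|---|---|---|---|
| 45% v 25% | 30% | 0.12 | 6% | 5.2% | 5.0% |
| 45% v 25% | 60% | 0.23 | 12% | 6.6% | 5.1% |
| 45% v 25% | 100% | 0.38 | 19% | 9.2% | 5.2% |
| 70% v 20% | 30% | 0.28 | 14% | 7.2% | 5.3% |
| 70% v 20% | 60% | 0.55 | 28% | 13.4% | 5.2% |
| 70% v 20% | 100% | 0.93 | 46% | 29.4% | 4.9% |

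With log fat added, the mean estimate lies within 0.01 of zero in every row. With equal prevalence (50% v 50%) the bias is zero without it.

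**Does the OSA adjustment absorb it?** I added a binary OSA covariate driven by fat, with an assumed latent correlation of 0.5, and let the whole gap run through fat. The bias fell from 0.47 to 0.45 at 50% v 25%, and from about 0.93 to 0.89 at 70% v 20%. A stronger OSA-fat link would absorb more.

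**Precision.** Over these scenarios the SD of the estimate is 0.63–0.64 with the steatosis term only, and 0.54–0.69 with log fat added. Power for a true difference of 2 after adjustment runs from 0.81 (70% v 20%, 30% share) to 0.95 (45% v 25%, 100% share). Precision improves when the within-stratum fat-flux correlation is about 0.55. It worsens when that correlation is about 0.2 to 0.35 and the imbalance is large.

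**The case against.** The strongest objection is causal direction. All the bias figures take liver fat as a driver of flux. The protocol's background leans at least partly the other way: section II.b proposes that pathway output shifted towards lipogenesis produces the excess fat, the preliminary data tie hepatic fat in PCOS to lipogenesis markers, and triglyceride synthesis is itself a primary outcome. Liver fat would then be partly a consequence of the outcome, and adjusting for it would remove real PCOS effect.

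I checked this with a true PCOS effect of 2, an assumed flux-log-fat correlation of 0.7 and no path from fat to flux, which implies prevalences of about 50% v 24%. The steatosis-stratified estimate averages about 1.4 and the fat-adjusted one about 1.0. At a correlation of 0.8 they are about 1.2 and 0.7. Matching on status attenuates too, but adjustment attenuates more. This stands: a reader might infer that the fat-adjusted coefficient is the hormonal effect and should replace the planned estimate, and the documents do not support that. If liver fat lies on the path from PCOS to flux, the adjusted coefficient is a direct effect only.

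Other points also stand in part. The 50–70% and 20–30% figures are for adult women. The binary reading of steatosis status is inferred from the have-or-have-not wording and the pilot-table cut. Hepatic fat is not ignored, since the separate regression uses it, but as described that regression does not estimate the PCOS-control difference. The point touches one secondary contrast; the primary comparison by steatosis within PCOS is unaffected.

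**Conclusion.** The inference from matching to hormonal state alone is not justified and should be corrected. If liver fat drives flux and its distribution is shifted upward in PCOS, the leftover bias is about 0.1 to 0.9 µmol/min/kg FFM (6% to 46% of the planned difference), with false-positive rates from about 5% to 29%. The range rests on the normal, equal-SD model for log fat, on the assumed share of the steatosis gap that runs through fat amount, and on prevalences partly taken from adults. The bias is zero if fat is equal within strata or if steatosis acts only as a step.

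Two stronger readings are tempting. One is that the bias is certain and its size known; the documents give neither the within-stratum slope nor the fat distribution by group. The other is that the categorical match costs precision or that the power is misstated; 0.87 reproduces, and adjustment can raise or lower precision.

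**What to change.** In Secondary Aims a):

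1. Keep the steatosis-matched comparison, analysed with a steatosis stratum term, and state the cut used for matching.
2. Prespecify a second model that adds log MRI fat fraction as a continuous covariate, with the steatosis term retained so that a step at the cut is still allowed for.
3. Report the PCOS coefficient with its confidence interval from both models, and the fat-fraction difference between groups within each steatosis stratum.
4. Attribute the difference to hormonal state only if it persists in the fat-adjusted model. State that attenuation alone does not rule out a hormonal effect, because liver fat may be a consequence of flux or lie on the path from PCOS to flux.
5. Remove the claim that matching leaves just the hormonal state.

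The cost is a few sentences, one model degree of freedom and a log-linear assumption within strata. No new data are needed. Because the adjusted estimate may be attenuated or a direct effect only, it belongs beside the matched estimate and not in its place.

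### The secondary powers of 0.87 hold only if hepatic steatosis (HS) is in the analysis model, and the plan does not put it there

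*Combined protocol and SAP*

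**What the plan says.** All of the power text is in section VII, Data Analysis Plan.

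- **Primary aim (HS against no HS).** "Utilizing the PEP value, from this paper, the difference between the group means is 3", with an SD of 2, both in µmol per minute per kg fat-free mass. The source compared men with and without HS. The plan continues: "With 15 untreated PCOS with HS and 15 untreated PCOS without HS, we would have a power of 0.97".
- **Secondary aim a), PCOS against controls.** "For comparison of the PCOS to control groups, individuals will be matched in terms of HS status", so that only the hormonal state differs. The inputs are a difference of 2 and an SD of 2, and the plan states that "with 20 PCOS and 20 controls, we would have a power of 0.87 to detect a alpha of 0.05".
- **Secondary aim b), each treatment against untreated PCOS.** The inputs are "with a difference of 2 Umol.min.kg FFM, and the standard deviation is 2, with 30 PCOS and 15 in a treatment group", again with 0.87. Nothing is said about matching on HS or adjusting for it.
- **Analysis.** PCOS and controls are to be compared by t test, or Mann-Whitney if the data are not normal. All measures are adjusted for OSA status or AHI severity, and for ethnicity if the groups differ. HS is not listed as a covariate, stratum or pairing factor for these group comparisons.
- **Group sizes.** Section III.B and the enrollment table in section III.C plan 20 completers in each of four groups.

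**The concern.** The primary calculation treats HS as a strong determinant of the outcome: a gap of 3 against an SD of 2. The secondary calculations keep the SD of 2 for groups that contain girls both with and without HS. If HS moves the outcome by 3, the spread within a mixed group must exceed 2 unless the analysis removes the HS part.

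In a), matching balances HS between the groups. An analysis that ignores the matching factor still leaves the HS variance in the error term. The test is then conservative, the intervals are wider than they need be, and the power gained by matching is lost. In b) the handling of HS is not stated, so the power cannot be read without a further assumption. At stake is whether these two comparisons have the power claimed, and whether a null result from either could be interpreted.

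**Working it through.** **Inputs from section VII:** HS effect 3; SD 2 within an HS group (read so because it accompanies a comparison of HS groups); secondary difference 2; sizes 20/20 and 30/15; alpha 0.05, taken as two-sided because one-sided gives 0.93 and does not match.

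**HS share p.** The primary aim's 15 + 15 gives p = 0.5 in the untreated PCOS pool. Section VIII reports more than 45% NAFLD in the team's obese girls with PCOS. Section II b) gives 20-30% for obese women without PCOS. No share is given for the treated groups.

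**Step 1: reproduce the plan.** Noncentral t, with noncentrality = difference / (SD × √(1/n1 + 1/n2)).

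- Primary, 15/15, difference 3, SD 2: 0.977 (stated 0.97).
- a) 20/20, difference 2, SD 2: 0.869 (stated 0.87).
- b) 30/15, difference 2, SD 2: 0.871 (stated 0.87).

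**Step 2: SD of a mixed group.** SD = √(2² + 3² × p(1 − p)).

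- p = 0.5: √(4 + 2.25) = 2.5.
- p = 0.25: √(4 + 1.6875) = 2.39.
- p = 0.70: √(4 + 1.89) = 2.43.

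**Step 3: t test without HS, HS status random, same p in both groups.**

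| p | SD | 20/20 | 30/15 |
|---|---|---|---|
| 0.25 | 2.39 | 0.734 | 0.736 |
| 0.50 | 2.50 | 0.693 | 0.696 |
| 0.70 | 2.43 | 0.719 | 0.722 |

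**Step 4: aim a) as designed, exactly matched on HS.** Simulation of 100,000 trials, 20/20, HS effect 3, residual SD 2.

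| Analysis | Power | Type I error |
|---|---|---|
| t test, 50% HS | 0.725 | 0.014 |
| t test, 40% HS | 0.73 | 0.015 |
| t test, 25% HS | 0.76 | 0.020 |
| HS as covariate (37 df) | 0.868 | 0.05 |
| Paired on HS (19 df) | 0.851 | – |

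The t test uses an SD of about 2.5 where the matched difference varies with SD 2, so at 50% HS its intervals are about 2.5 / 2 = 1.25 times as wide as they should be.

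**Step 5: aim b) when HS shares differ (no HS in the model).** At 30/15 with 15 of 30 untreated girls having HS, power is 0.78 with 7 of 15 treated girls having HS and 0.68 with 8 of 15. At 20/20, assume 50% HS untreated and 25% treated. If the HS imbalance adds to the treatment effect, the expected difference is 2 + 3 × 0.25 = 2.75 and power is about 0.96. If it opposes the effect, the difference is 2 − 0.75 = 1.25 and power is about 0.32. With HS in the model and balanced, power is 0.868 at 20/20 and 0.871 at 30/15.

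**The case against.** The strongest reply is that the plan made no mistake in its sums. The two 0.87 figures are correct for the inputs given, and the SD is offered openly as an assumption. That stands: a reader might infer an arithmetic error, and there is none.

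Second, a) is matched on HS, so SD 2 is the right input for an analysis that uses the matching. That also stands. A reader might carry the figure of 0.70 over to a), but it describes unmatched groups. Under matching, the t test without HS has about 0.73 to 0.76. What remains is that no such analysis is specified.

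Third, the planned analysis is not bare, because all measures are adjusted for OSA. Section II (preliminary polysomnogram data) reports a strong relation between OSA and fatty liver, so OSA would absorb some HS variance. The documents do not allow the amount to be computed. As an illustration only, with an assumed OSA-HS correlation of 0.35 to 0.6, 50% HS, 20/20 and OSA but not HS in the model, power is about 0.71 to 0.76. OSA adjustment would then not substitute for HS.

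Fourth, for b) the 0.70 needs equal HS shares, which the plan does not state. Section I says that metformin decreases HS, so the shares may well differ. This stands, and it makes any single power figure for b) conditional.

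Finally, the inputs of 3 and 2 come from 6 men with HS and 13 without, so their transfer to adolescent girls is uncertain. That is fair, but the plan relies on the same inputs for every power it states.

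**Conclusion.** The power assumption and the named analysis do not fit each other. The figure of 0.87 requires HS in the model.

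- **a)** Without HS in the model, power is about 0.73 at 50% HS and 0.76 at 25%, and type I error is 0.01 to 0.02. With HS, the figures are 0.87 and 0.05. This assumes exact matching, an HS effect of 3, residual SD 2, and leaves OSA adjustment aside.
- **b)** Without HS in the model, power is about 0.70 if treated and untreated girls share an HS rate near 50%. It rises or falls if the rates differ. It is not supported to say flatly that b) lacks its stated power.

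A reader might also blame the 30/15 split for the loss. It does not cause it: at SD 2.5, power is 0.696 at 30/15 and 0.693 at 20/20. The split is still wrong for the study, because sections III.B and III.C plan 20 per group.

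This should be fixed but does not block the study. The comparisons are secondary, the primary HS comparison is unaffected, and in a) the test errs on the conservative side, so there is no added risk of a false positive from this source.

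**What to change.** - **a)** Name a linear model with group and HS status (the matching factor), together with the planned OSA adjustment and, where it applies, ethnicity. State that the 0.87 refers to this model.
- **b)** Restate the power for 20 against 20 in place of 30 against 15, with its assumption: about 0.87 with HS in the model and balanced between groups, or about 0.69 without HS if both groups are near 50% HS. Add that the figure moves in either direction if the HS shares differ.
- **b), reporting.** Give HS-adjusted and unadjusted estimates side by side. Metformin may act partly through HS, so the adjusted estimate alone could remove part of the effect of interest, and the unadjusted one alone mixes it with HS differences between non-randomised groups.

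The cost is a few lines in section VII and one degree of freedom. Liver fat is already planned by MRI in all 80 completers, so no new measurement or participant is needed. The price is one stated power that becomes conditional and possibly less favourable.
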